1) Experimental Design: Subjects will be studied in random order (at least 2 weeks apart) during which they will be infused with either Exendin-9,39 or saline during the study. On each occasion, subjects will be admitted at approximately 0600, to the Mayo Clinic outpatient CRTU (Charlton Building) on the morning of study after an overnight fast of 8 hours. At approximately 0615 (-210 min), a cannula will be inserted retrogradely into a vein of the dorsum of the hand. This will be placed in a heated Plexiglas box maintained at 55°C to allow sampling of arterialized venous blood. A cannula will also be placed in the vein of the contralateral hand to allow infusions (Fig.10). Prior to study start at approximately 0720 (-10 min) subjects will use a Visual Analog Scale (VAS) to measure appetite and hunger (57). At approximately 0730 (0 min) subjects will consume a mixed meal consisting of one scrambled egg, 15 g of ham, and Jell-O containing 35 g of glucose. The egg will be labeled with 0.5 mCi ^{99m}Tc-sulfur colloid to enable measurement of gastric emptying as before (58). At this time, (0 min) an infusion of saline will start and continue till the end of the study. The meal will occupy a volume that is tolerable to patients who have undergone restrictive upper gastrointestinal surgery. Blood will be collected to measure glucose and hormone concentrations. **Gastric Emptying:** Anterior and posterior gamma camera images will be obtained immediately after ingestion of the radiolabeled meal, every 15 min for the first 2 h, then every 30 min for the next 2 h (total 4 h after the radiolabeled meal), as before (50; 52; 53; 59). **VAS scores and free-choice caloric intake:** will be measured at 30 minute intervals for the remainder of the study (44). At approximately 1130 (240 min) a free-choice standard buffet (consisting of lasagna, pudding and milk) will be placed in the room. The amount of items eaten from the buffet (including partially consumed buffet items) will be recorded. The study will end at 1230 (300 min) when infusions will be stopped, cannulae removed and the subject can then leave the CRTU. On the **Exendin-9,39** study day, at 0 min (0730), Exendin-9,39 will be infused @ 750 pmol/kg/min (following a bolus of 2250 pmol/kg administered at time 0 – as before (54)), for 1 hour (0-60 min). The rate of Exendin-9,39 will be decreased to 300 pmol/kg/min for the next 3hours (61-240 min). At that time, the rate will be increased to 750 pmol/kg/min for the remainder of the study (241-300- min).

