
1) Power Calculation: In a prior experiment we observed an overall mean value \pm (SD) of Gastric Emptying = $145 \pm (27)$ min(60) and $745 \pm (86)$ Cal(44). Assuming similar variation, 25 subjects per group would provide approximately 85% power (at a 2-sided 0.05 α level), to detect a 15% change in GE₅₀ (time taken to empty 50% of gastric contents) and a 10% change in caloric intake in each group in response to Exendin-9,39.

1) Statistical Analysis: Data will be presented as (observed) mean \pm SEM. The initial analyses will compare the within-group effect of treatment (Exendin-9,39) with the data observed in the study where saline is infused. This analysis will use a paired t-test, or signed-rank test, as warranted. An ANCOVA model incorporating the corresponding baseline study value as a covariate (e.g. GE₅₀) will be used to test differences in the response to Exendin-9,39 between groups (RYGB vs. SG). The ANCOVA model will also include age, gender and weight as covariates. A p -value < 0.05 will be considered to be statistically significant.

1) Interpretation: We will test the hypothesis that blockade of the GLP-1 receptor (GLP1R) in subjects after RYGB increases caloric intake to amounts that do not differ from those consumed after SG in the presence or absence of Exendin-9,39 infusion. We anticipate that after RYGB, subjects presented with a free choice buffet will eat less than subjects after SG during saline infusion. However, Exendin-9,39 increases caloric intake during a free choice buffet after RYGB. This supports the suggestion that the high concentrations of GLP-1 observed after RYGB alters feeding behavior, decreasing caloric intake. Given the lower concentrations of GLP-1 observed after eating in SG, we anticipate that Exendin-9,39 will have little effects, if any, on caloric intake in subjects post-SG.

To test our secondary hypothesis, we will measure gastrointestinal transit using a labelled meal as outlined above during the two studies. We anticipate that in subjects after RYGB, inhibition of endogenous GLP-1 by Exendin-9,39 will accelerate gastrointestinal implying that the high concentrations of GLP-1 observed after RYGB delay gastrointestinal transit. Conversely, in the absence of very significant elevations in endogenous GLP-1 after SG, we expect little effect of Exendin-9,39 on gastrointestinal transit – as observed previously in subjects with an intact upper gastrointestinal tract (1).

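### The written infusion schedules differ between the Exendin-9,39 and saline days and no masking is described, so free-choice intake and VAS after 0 min are open to expectation bias

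*Combined protocol and SAP*

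**What the plan says.** All of the infusion detail is in Experimental Design (section IV). Each subject has two study days in random order, at least 2 weeks apart.

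- **Saline:** "At this time, (0 min) an infusion of saline will start and continue till the end of the study". No bolus or rate change is given. The sentence stands in the account of what happens on each occasion, so it can be read as applying to both days.
- **Exendin-9,39 day only:** an infusion from 0 min ("following a bolus of 2250 pmol/kg administered at time 0"), a lower rate for 61-240 min, then "At that time, the rate will be increased to 750 pmol/kg/min for the remainder of the study" (241-300 min). The buffet is placed at about 240 min.
- **Outcomes:** subjects rate appetite and hunger by VAS at -10 min and at 30-minute intervals during the study. For the buffet, "The amount of items eaten from the buffet (including partially consumed buffet items) will be recorded"; the recorder is not named.

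No visible section says that the subject, bedside staff or buffet recorder is masked. The only mention of a double-blind design is in the title of a cited study (reference 44). The codes under Confidentiality (section V) identify subjects, not infusions. That section also places IV infusions in the medical record, without saying whether the product is named.

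**The concern.** Free-choice intake is the subject of the primary hypothesis. It depends on what a subject decides to eat and on how a person records what is left. VAS is self-report. Knowledge of the treatment can move either.

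The plan also commits the investigators to a direction. Specific Aims and Interpretation expect Exendin-9,39 to raise intake after RYGB, and Interpretation expects little effect after SG. Awareness among staff could therefore produce the predicted pattern. Random order protects against period effects, not against knowledge of which infusion is running.

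At stake are three comparisons: the within-group test of Exendin-9,39 against saline, the between-group ANCOVA, and the primary hypothesis that blockade in RYGB "increases caloric intake to amounts that do not differ from those consumed after SG in the presence or absence of Exendin-9,39 infusion".

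**Working it through.** **1. What each day looks like at the bedside, as written**

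| Time | Exendin-9,39 day | Saline |
|---|---|---|
| 0 min | bolus, infusion starts | infusion starts |
| after 60 min | rate lowered | no change described |
| about 240 min, buffet placed | rate raised | no change described |
| 300 min | stopped | stopped |

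If saline runs on both days, the bolus and the two steps still belong to one day only. The -10 min VAS precedes the infusion, so this pattern cannot affect it.

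**2. The plan's own figure**

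Power Calculation gives intake of 745 (SD 86) Cal, a 10% change (74.5 Cal), two-sided 0.05, and "25 subjects per group would provide approximately 85% power". A two-sample t-test with 25 per group has noncentrality 74.5 / (86 × √(2/25)) = 3.06 and 48 df, which gives power 85.1%. A paired t-test with within-subject correlation ρ = 0 has the same noncentrality and 24 df, which gives 83.6%. The stated figure reproduces for intake.

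**3. Where a shift enters the analysis**

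Suppose awareness adds *b* Cal to the Exendin-day value.

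- *Within-group comparison.* The plan states: "This analysis will use a paired t-test, or signed-rank test, as warranted". The mean paired difference moves by *b*.
- *RYGB on Exendin-9,39 against SG on saline.* This difference also moves by *b*.
- *ANCOVA, reading the baseline study value as the saline-day value.* The covariates do not change and the least-squares estimate is linear in the outcome. A shift common to both groups therefore goes into the intercept and cancels from the group coefficient. A RYGB-only shift adds *b* to that coefficient in full. This is algebra and says nothing about whether a shift occurs.

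**4. Illustration for the paired test, no drug effect**

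The SD of the paired difference is 86 × √(2(1 − ρ)). The noncentrality is *b* × √25 / SD of difference, with 24 df and two-sided 0.05. The documents give neither *b* nor ρ; both are assumed here.

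| | ρ = 0 | ρ = 0.5 | ρ = 0.75 |
|---|---|---|---|
| SD of difference (Cal) | 121.6 | 86.0 | 60.8 |
| 1% shift, 7.45 Cal | 6% | 7% | 9% |
| 2.5% shift, 18.6 Cal | 11% | 18% | 31% |
| 5% shift, 37.25 Cal | 31% | 55% | 84% |

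For example, at ρ = 0.5 a 5% shift has noncentrality 37.25 × 5 / 86 = 2.17, and the test is significant in 55% of trials.

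The stated 85% does not fix ρ. For intake, a paired test reaches 85% at ρ of about 0.04, but the two-sample formula gives 85.1% with no ρ at all. The same 85% claim covers GE₅₀ (15% of 145 = 21.75 min, SD 27), where a paired test needs ρ of about 0.17. The whole range is therefore shown. At ρ = 0.5 and 0.75, paired power for the 10% change would be 98.6% and above 99.9%, well above the plan's figure.

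**The case against.** **The documents are silent, not open-label.** A reader might infer that the study is unmasked. The text does not say so. Saline could serve as a masked placebo. Fig. 10, cited where the infusion cannula is described, and the title and consent pages could not be checked, and any of them might describe masking or the infusion scheme. This stands, and it limits the point to what is written. It does not dispose of it, because a statement of masking would not be enough if the pump schedules still differed as described.

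**Subject awareness is conjecture.** Nothing shows that a subject would notice a bolus or a pump change, or is told the expected direction. The Hormone Infusion paragraph (section V) reports that earlier use does not suggest specific adverse events such as nausea, which counts against unmasking by sensation. This stands: awareness is clear only for staff who handle the infusion, and merely possible for subjects.

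**The percentages are the test's power for invented shifts.** Correct. A reader might take them as false-positive rates for this trial, and they are not. For a 1% shift the rate stays near nominal. They show sensitivity, not evidence of bias.

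**A request for clarification would suffice.** This stands only in part. The two schedules differ in the text itself, so the saline-day procedure needs matching or confirmation as well as a sentence on masking.

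**Conclusion.** The concern holds as a risk created by the written schedules and the absence of any visible masking statement. Followed as written, staff handling the infusion can tell the two days apart while intake and the VAS ratings after 0 min are collected. Scintigraphic gastric emptying is much less exposed.

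The size of any bias is unknown. Under the assumptions shown (no drug effect, SD 86 Cal, n = 25, ρ from 0 to 0.75), the paired test would be significant in about 6-9%, 11-31% or 31-84% of trials for shifts of 1%, 2.5% or 5%. The SD comes from a study that, by its title, was in type 2 diabetes, and may not fit subjects after bariatric surgery. No rejection rate is claimed for the ANCOVA, where only a shift that differs between the groups matters.

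A reader might go further and conclude that a rise in intake after RYGB would be an artefact. The documents do not support that. The point is that the plan, as it reads, could not rule out a contribution from expectation. It should be addressed; confidence is medium because masking may be described in material that could not be checked.

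**What to change.** - State who is masked: subject, bedside staff and buffet recorder.
- On the saline day, give a volume-matched saline bolus and pump-volume steps at the same clock times as on the Exendin-9,39 day. The Exendin-9,39 regimen is unchanged.
- Have the personnel who already prepare the infusates issue coded, visually identical preparations, and chart the infusion under its code until unmasking.
- Record buffet intake and convert it to calories before the code is opened.
- If masking is already planned or shown in Fig. 10, say so in the text and confirm that the saline-day pump program matches.

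The cost is protocol wording, coded labels and chart entries, and a matched pump program, with no added visits or subjects. The downside is that the preparer must hold the code and an emergency unmasking procedure is needed.

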1. Abstract

Both Sleeve Gastrectomy (SG) and Roux-en-Y Gastric Bypass (RYGB) increase GLP-1 concentrations, although this is of lesser magnitude in SG compared to RYGB. We have data to suggest that endogenous GLP-1 is at least partially responsible for reducing free-choice caloric intake after RYGB, providing a mechanism underlying differences between procedures. Inhibition of GLP-1 action with Exendin-9,39 after RYGB accelerates gastric emptying. These observations suggest that factors other than anatomy regulate the upper gastrointestinal response to food ingestion. It is therefore reasonable to consider that the postprandial rise in GLP-1 might affect feeding behavior after RYGB, and to a lesser extent SG, where the increase in GLP-1 is less marked.

Title:	Exendin (9,39) and Satiety After Bariatric Surgery
Funding Source/Grant No.:	Obesity Society
IRB Number:	
IRB Approval Date:	
Principal Investigator:	[name] MD
Co-investigator(s):	[name] MD; [name] MD

I. Hypothesis and Specific Aims

The *overall aim* of this application is to determine the contribution of the elevated incretin hormone concentrations seen after certain types of bariatric surgery to the regulation of food intake and satiety. Roux-en-Y Gastric Bypass (RYGB) and sleeve gastrectomy (SG) are the commonest forms of bariatric surgery and raise Glucagon-like Peptide-1 (GLP-1) secretion although to markedly different degrees. Recently, we demonstrated that inhibition of GLP-1 actions by Exendin-9,39 accelerates gastrointestinal transit implying a role of GLP-1 in gastrointestinal function after gastric bypass (1). Given that GLP-1 affects upper gastrointestinal function, it seems reasonable to postulate that GLP-1 may play a role in food intake after gastric bypass (2; 3). In support of this we have generated preliminary data to show that Exendin-9,39 increases oral intake after bariatric surgery.

Specific Aim: Determine the effects of GLP-1 Receptor blockade on caloric intake and gastrointestinal transit in subjects after SG and after RYGB.

1° Hypothesis: Blockade of the GLP-1 receptor in subjects after RYGB produces equivalent caloric intake to that observed after SG.

2° Hypothesis: Blockade of the GLP-1 receptor accelerates gastrointestinal transit in subjects after RYGB but not after SG.

[figure not shown]
II. Background and Significance

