Study Subjects: A total of 50 subjects (25 post-RYGB and 25 post-SG) will be recruited. We will recruit otherwise healthy subjects who have undergone bariatric surgery within the past 10 years... We will exclude subjects with diabetes post-bariatric surgery. Healthy status will indicate that the participant has no known active systemic illness and no history of symptomatic microvascular or macrovascular disease. To be eligible subjects must be willing to participate in all the studies outlined. **Screening Visit:** Subjects will provide written informed consent. To ensure they are healthy, subjects will undergo a history and physical examination; blood collection for complete blood count and chemistry group; urine collection to exclude pregnancy, vital signs, blood pressure, pulse, height and weight.. Habitual activity levels (55), and bowel symptoms (56) will be assessed. **Body Composition:** % body fat will be measured using dual-energy X-ray absorptiometry (iDXA scanner; GE, Wauwatosa, WI).

Exclusion Criteria: Subjects <20 years of age will not be studied to minimize the possibility of type 1 diabetes. Subjects > 70 years of age will not be studied to minimize the potential confounding effects of age on glucose tolerance. Healthy status will indicate that the participant has no known active systemic illness.

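### The 85% power is a within-group figure, yet the primary claim is RYGB–SG equivalence with no margin and only p < 0.05 as criterion, so a non-significant difference could pass as support

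*Combined protocol and SAP*

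**What the plan says.** The primary hypothesis (section I) is a comparison between surgical groups: "Blockade of the GLP-1 receptor in subjects after RYGB produces equivalent caloric intake to that observed after SG". The Interpretation paragraph in section IV restates it as RYGB intake rising under blockade to amounts no different from SG intake. The secondary hypothesis expects faster transit after RYGB and not after SG.

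On size, section IV says "A total of 50 subjects (25 post-RYGB and 25 post-SG) will be recruited". The Power Calculation cites a prior mean of 745 Cal (SD 86) for intake and 145 min (SD 27) for gastric emptying. It states that "25 subjects per group would provide approximately 85% power (at a 2-sided 0.05 α level") "to detect a 15% change in GE₅₀" and "a 10% change in caloric intake in each group in response to Exendin-9,39".

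The Statistical Analysis paragraph has two parts. First come within-group paired tests of Exendin-9,39 against saline. Then an ANCOVA with the corresponding baseline study value, age, gender and weight as covariates "will be used to test differences in the response to Exendin-9,39 between groups (RYGB vs. SG"). The only decision rule is a p-value below 0.05. No equivalence margin, between-group power or detectable between-group difference is given, and no correlation between the two study days.

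**The concern.** The one number that justifies the sample size concerns a change inside a group, while the primary conclusion concerns RYGB against SG. The within-group power does not carry over to that comparison.

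The direction of the primary hypothesis makes this matter more than an ordinary omission. The hoped-for result is no difference between the groups under blockade. With p < 0.05 as the only rule, the natural way to find support is a non-significant RYGB-versus-SG test. Imprecision then works in favour of the hypothesis, and the 85% invites the reader to trust a null result from a test for which no power was calculated.

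**Working it through.** **Inputs from section IV.** n = 25 per group; two-sided α = 0.05; intake 745 Cal, SD 86; 10% of 745 = 74.5 Cal. Not in the documents: the correlation r between a subject's two study days, and the size of any saline-day gap between groups. Both are varied below. Equal SDs in both groups and on both days, and no dropout, are assumed. All power figures use the noncentral t distribution.

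**1. The plan's figure.** Paired t-test, SD of the difference = 86 × √(2(1 − r)). At r = 0 this is 121.6, the SE is 121.6/√25 = 24.32, and 74.5/24.32 = 3.06. With 24 df the power is 83.6% (86.5% by normal approximation). The stated 85% is reproduced as a within-group figure with the two days treated as nearly uncorrelated. At r = 0.3 and 0.5 the paired test has 94.0% and 98.6%. For gastric emptying (15% of 145 = 21.75 min, SD 27) the paired test at r = 0 gives 78.0% (81.3% normal).

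**2. Precision of the primary contrast (RYGB minus SG intake under Exendin-9,39).** SE = 86 × √(2/25) = 24.32 Cal. The 95% CI half-width is 2.011 × 24.32 = 48.9 Cal, and 48.9/745 = 6.6%. No correlation enters, because the contrast compares levels in two independent groups.

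**3. How often a real difference would look like none.** For a true 5% difference (about 37 Cal), 37/24.32 = 1.52. With 48 df the test is non-significant about 68% of the time.

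**4. Power for a 74.5 Cal difference in response between groups.**

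- *Planned ANCOVA.* If RYGB eats g Cal less than SG on saline, the Exendin-day difference is 74.5 − g, and the adjusted effect is 74.5 − (1 − r)g. The SE is 86 × √(1 − r²) × √(2/25) × √(1 + (g/86)²/4), with 44 df after four covariates. The last factor is √1.047 for g = 37.25 and √1.188 for g = 74.5.
- *Change-score t-test.* SE = 86 × √(2(1 − r)) × √(2/25), with 48 df.

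| Analysis | r = 0 | 0.3 | 0.5 | 0.7 |
|---|---|---|---|---|
| ANCOVA, no saline gap | 85.0% | 88.1% | 93.3% | 98.7% |
| ANCOVA, gap 37.25 Cal (assumed) | 31.0% | 51.4% | 71.8% | 93.6% |
| ANCOVA, gap 74.5 Cal (assumed) | 5.0% | 13.9% | 35.5% | 76.9% |
| Change-score test (not planned) | 56.4% | 71.8% | 85.1% | 97.2% |

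Example: with g = 74.5 and r = 0.5 the adjusted effect is 37.25 and the SE is 22.96; the ratio 1.62 gives 35.5%. Simulations of the ANCOVA with the 74.5 Cal gap gave 5%, 13%, 33% and 73%, in line with that row.

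Power falls with the gap because the surgical groups are not randomised. Adjusting for saline-day intake then removes part of the contrast the investigators want to see. Section IV does expect RYGB to eat less on saline, but gives no amount.

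**The case against.** The strongest defence is that the plan never claims 85% for a between-group test. The figure is explicitly for each group, it matches the paired tests listed first, and the Specific Aim is about the effect of blockade in both kinds of patient. That stands: the 85% is correctly computed for what it describes, and the fault is not one of arithmetic.

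A reader might go further and infer that the between-group comparison has only 56% power and reaches 85% only if r is 0.5 or more. The documents do not support that. Those figures belong to a t-test on change scores, which is not planned. The planned ANCOVA with equal saline means has 85.0% for calories already at r = 0, and a plain comparison of intake levels has 85.1% for a 74.5 Cal difference whatever r is.

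A reader might also treat the 5–77% row as the plan's own scenario. It is not: the direction of the gap comes from the plan, but 74.5 Cal is an assumed size, and half that gap gives 31–94%.

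Finally, nothing in the text says outright that non-significance will be called equivalence. But the primary hypothesis is worded as equivalence, the Interpretation paragraph as absence of difference, and no other criterion is supplied. None of these defences provides a basis for an equivalence conclusion. Power to detect a difference, by any model, does not establish equivalence.

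**Conclusion.** The concern holds in this form: the 85% is a within-group figure and supports no RYGB-versus-SG conclusion, and the primary hypothesis has no margin against which it could be shown. On the plan's inputs the between-group difference in intake would be known to about ±49 Cal (6.6% of 745), and a true 5% difference would pass as non-significant about two times in three.

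These two figures rest on an SD of 86 Cal applying to both post-surgical groups and on no dropout; a larger SD widens the interval in proportion. Between-group power for a 74.5 Cal difference in response cannot be reduced to one number, since it depends on the model, r and the saline gap. It would be wrong to conclude that the trial is underpowered for that test, or that it needs more subjects. The documents establish neither.

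**What to change.** In section IV:

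- Label the 85% in the Power Calculation as power for the within-group Exendin-9,39 versus saline comparison only.
- In the Statistical Analysis, report the RYGB-versus-SG difference in intake under Exendin-9,39 as an estimate with a 95% CI.
- State that a non-significant result will not be read as equivalence or as no difference. Claim equivalence only if that CI lies wholly within a margin the sponsor states in advance. At the assumed SD, a margin below about 49 Cal could hardly be met.
- If between-group power is quoted, give it for the planned ANCOVA with its assumed correlation and saline-day gap. The change-score figures should not be printed beside a different planned test.

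The cost is a few sentences and the choice of a margin, with no extra subjects, visits or procedures. The downside is that the primary claim becomes harder to make. Purely as an illustration, with a margin of 74.5 Cal and a true difference of zero, the 95% CI would fall inside the margin about 73% of the time (2Φ(74.5/24.32 − 1.96) − 1, normal approximation).

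### The two-visit crossover is analysed without a period or order term and the order balance is not stated, so any visit-to-visit shift in buffet intake costs power and, if the realised order is uneven, causes bias

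*Combined protocol and SAP*

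**What the plan says.** The Experimental Design part of section IV sets out a two-period crossover within each surgery group: "Subjects will be studied in random order (at least 2 weeks apart"). Section V, Detailed Description, repeats this. Neither place gives a method of randomisation, a block size, an allocation ratio or stratification by type of surgery.

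The Statistical Analysis paragraph compares Exendin-9,39 with saline inside each group: "This analysis will use a paired t-test, or signed-rank test, as warranted". The two groups are then compared by an ANCOVA on the corresponding baseline study value, and "The ANCOVA model will also include age, gender and weight as covariates". Period and order appear in neither analysis, and no other section supplies them.

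On size, the Power Calculation states that "25 subjects per group would provide approximately 85% power" ("at a 2-sided 0.05 α level") for "a 10% change in caloric intake in each group in response to Exendin-9,39".

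**The concern.** Subjects go through the same cannulation, heated box, test meal and buffet twice. Intake could plausibly rise or fall at the second visit whatever is infused. A paired test has no place for such a shift. It adds P to the Exendin-minus-saline difference when Exendin comes second and subtracts P when it comes first. Two consequences follow.

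- The shift inflates the variance of the differences, so power falls even when order is perfectly balanced.
- If more subjects receive one order than the other, part of the shift is counted as drug effect. In the between-group ANCOVA a common shift cancels when both groups have the same order split, and biases the comparison when they do not.

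Lost power matters here because the Interpretation section expects RYGB intake under Exendin not to differ from SG intake, and expects little effect of Exendin after SG. Avoidable noise makes non-significant results more likely and so favours those readings.

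**Working it through.** **Inputs from the plan.** n = 25 per group; two-sided 0.05; caloric intake 745 (SD 86) Cal; effect 10% × 745 = 74.5 Cal.

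**Assumed, because the plan gives no value.** The between-visit correlation is taken as 0 or 0.5. The SD of differences is 86 × √(2(1−ρ)), which is 121.6 Cal at ρ = 0 and 86 Cal at ρ = 0.5. The shift P is taken as 0, 37.25 (5% of 745) or 74.5 Cal (10%).

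**The plan's own figure.** A paired t-test with SD 121.6 and 24 df has noncentrality 74.5/(121.6/√25) = 3.06 and power 83.6%. A two-sample t-test with SD 86 and 48 df gives 85.1%. The stated 85% is therefore reproduced at about zero correlation. With SD of differences 86 the paired power is 98.6%.

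**Within group, averaged over simple randomisation.** Each difference is effect ± P + error, so its SD becomes √(SD² + P²).

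- SD 121.6: √(14,787 + 1,388) = 127.2 at P = 37.25, and √(14,787 + 5,550) = 142.6 at P = 74.5.
- SD 86: 93.7 and 113.8.

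The period-adjusted estimate is the average of the two order-specific mean differences. Its standard error is (SD/2)√(1/n1 + 1/n2), which does not depend on P. Simulated power (60,000 runs):

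| SD of differences | Analysis | P = 0 | P = 37.25 | P = 74.5 |
|---|---|---|---|---|
| 121.6 | paired t | 83.5% | 80.0% | 70.6% |
| 121.6 | period-adjusted | 81.8% | 81.7% | 81.8% |
| 86 | paired t | 98.6% | 96.8% | 88.4% |
| 86 | period-adjusted | about 98% | about 98% | about 98% |

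The paired type I error averages about 5% throughout.

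**Within group, given the realised split.** Bias = P(n1−n2)/25; type I error is simulated. Ranges run over the two SDs.

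| Split | Chance of this or worse, simple randomisation | P | Bias (Cal) | Paired type I error |
|---|---|---|---|---|
| 15:10 | 42% | 37.25 | 0.20 × 37.25 = 7.5 | about 5% |
| 15:10 | 42% | 74.5 | 0.20 × 74.5 = 14.9 | 4–5% |
| 16:9 | 23% | 74.5 | 0.28 × 74.5 = 20.9 | 7–8% |
| 17:8 | 11% | 37.25 | 0.36 × 37.25 = 13.4 | 7–9% |
| 17:8 | 11% | 74.5 | 0.36 × 74.5 = 26.8 | 11–15% |

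At 16:9, P = 74.5 and SD 121.6, paired power is 93% or 44% depending only on the direction of the shift; adjusted power is 80%.

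**Balance alone is not enough.** At 13:12 the bias is only 0.04P, but the shift still counts as noise. With P = 74.5 and SD 121.6, the paired type I error is 2.3% and power 69–77%, against 83–84% adjusted.

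**Between-group ANCOVA** (20,000 runs, visit SD 86). This takes the saline-day value as the baseline study value, assumes no saline-day group difference and null effects of the other covariates, and uses 74.5 Cal as the between-group difference. With p1 and p2 the proportions receiving Exendin second in the two groups and b the fitted slope on the saline value, bias ≈ P(p1−p2)(1+b). For opposite 15:10 splits, ρ = 0 and P = 37.25: b = −0.24 × 37.25²/(86² + 0.24 × 37.25²) = −333/7,729 = −0.043, so bias = 37.25 × 0.2 × 0.957 = 7.1 Cal, which matches the simulation. Ranges below run over ρ = 0 to 0.5.

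- Averaged over simple randomisation: type I error about 5%. Power is 80–87% at P = 37.25 and 75–78% at P = 74.5, against 80–90% with an order term.
- Equal splits in both groups: no bias.
- Opposite 15:10 splits (order counts differing by 5 or more: 20% chance): bias 7–11 Cal at P = 37.25 and 13–19 Cal at P = 74.5; type I error 5.5–7%.
- Opposite 17:8 splits (differing by 9 or more: 1.5% chance): bias 13–19 Cal and type I error 8–12% at P = 37.25; 23–34 Cal and 12–22% at P = 74.5.
- With an order term: bias within 0.3 Cal and type I error about 5%.

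**The case against.** The strongest reply is that every loss above comes from an assumed P. The plan contains no evidence of a shift, and P = 74.5 Cal makes it as large as the whole planned drug effect. Both visits follow the same clock times, test meal and buffet. The paired test is unbiased over the randomisation and its average type I error is 5%. Clear inflation needs a badly uneven order together with a large shift. If order is left unblocked, the period term loses a little power until P reaches about 25–30 Cal (SD 121.6) or about 20 Cal (SD 86), and at P = 37 it gains under 2 points. The between-group figures rest on further assumptions: the plan expects RYGB subjects to eat less than SG subjects on saline, and it states the 10% effect only within each group.

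All of this is correct, and it limits the point to a precaution whose size is unknown. It does not remove it. Order is known for every subject, the trial will realise only one split per group, and a balanced split still leaves the shift in the error term. With blocking, the period term costs almost nothing if P is zero.

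**Conclusion.** The concern holds. Neither planned analysis accounts for period or order, and balance of order is not stated. The expected harm is lost power: about 3 to 4 points or less within group at a shift of 5% of intake, and about 10 to 13 points at 10%. Bias and excess type I error are conditional. In these scenarios type I error within a group clearly exceeds 5% only from about 16:9, and in the ANCOVA when the two groups' order splits differ. There is no inflation averaged over the randomisation. These sizes rest on assumed values of P and of the between-visit correlation, and the between-group figures also on the simplified ANCOVA described above. GE₅₀ is analysed by the same tests and is open to the same mechanism, but it was not quantified.

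**What to change.** - State how order is randomised, and block it within each surgery group (13:12 is the nearest to balance with 25).
- Replace the paired t-test with a crossover analysis containing treatment and period, or equivalently the average of the two order-specific mean differences (23 df).
- For non-normal data, replace the signed-rank test with a rank-sum test comparing visit 2 minus visit 1 differences between the two orders.
- Add order (Exendin first or second) as a covariate in the RYGB-versus-SG ANCOVA.

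The cost is SAP wording, a blocked order list and one degree of freedom; no extra visits or data are needed. With no period effect, the within-group analysis loses about 0–2 power points at 13:12 or 15:10 and about 5 at 17:8 (83.6% to 78.3%, SD 121.6). The ANCOVA loses about 0–2 points at 13:12 or opposite 15:10 splits and 4–6 at opposite 17:8 splits. Blocking avoids the larger losses. The period term is still needed with blocking, both to remove the shift from the error and because drop-outs can unbalance a blocked list.
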